6.1.2 Objective #2

6.1.2.1 REDACTED PPRU Antimicrobial PK Study

Data will be extracted from the medical record of participants enrolled at Redacted in the PPRU Antimicrobial PK in High Risk Infants study. The following clinical and demographic variables will be included in addition to date of birth, gestation age, race, ethnicity, sex, and birth weight (Table 2).

Table 2: Variables Collected for Redacted Safety Study

	Date of birth	-3 days	-2 days	-1 day	On ampicillin	+1 day	+2 days	+3 days
Demographics								
Weight	X			X		X		
Length	X			X		X		
Head circumference	X			X		X		
Adverse Events (new onset)								
Cardiorespiratory arrest					X			
Hypotension					X			
Tachypnea					X			
Tachycardia					X			
Medical NEC					X			
Surgical NEC					X			
Focal intestinal perforation					X			
Grade II IVH					X			
Grade III or IV IVH					X			
Periventricular leukomalacia					X			
Cystic periventricular leukomalacia					X			
PDA requiring medical treatment					X			
PDA requiring surgical treatment					X			
Rash					X			
Seizure					X			
ROP requiring laser surgery					X			
Hyperbilirubinemia requiring exchange transfusion					X			
Laboratory Values*								
AST		X	X	X	X	X	X	X
ALT		X	X	X	X	X	X	X
WBC count		X	X	X	X	X	X	X
Hematocrit		X	X	X	X	X	X	X
Platelets		X	X	X	X	X	X	X
BUN		X	X	X	X	X	X	X
Creatinine		X	X	X	X	X	X	X
Physical Exam								
Abnormality				X	X			
Positive Blood/Urine/CSF Cultures								
Organism		X	X	X	X	X	X	X
Antimicrobial sensitivities		X	X	X	X	X	X	X
Ampicillin dosing**								
Date/time					X			
Dose (mg)					X			

* If laboratory value obtained on start day of ampicillin course, time of day should be recorded.

** Only start of/changes in/last dose of ampicillin dosing/frequency associated with the ampicillin course in which PK samples were obtained will be recorded.

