6.1.2.2 Pediatrix Administrative Database Review

Data will be extracted from the Pediatrix Medical Group Database. The following clinical and demographic variables will be included in addition to date of birth, gestation age, race, ethnicity, sex, and birth weight (Table 3).

Table 3: Variables Collected for Pediatrix Safety Study

	Date of birth	-3 days	-2 days	-1 day	On ampicillin	+1 day	+2 days	+3 days
Adverse Events (new onset)								
Cardiorespiratory arrest					X			
Hypotension					X			
Tachypnea					X			
Tachycardia					X			
Medical NEC					X			
Surgical NEC					X			
Focal intestinal perforation					X			
Grade II IVH					X			
Grade III or IV IVH					X			
Periventricular leukomalacia					X			
Cystic periventricular leukomalacia					X			
PDA requiring medical treatment					X			
PDA requiring surgical treatment					X			
Rash					X			
Seizure					X			
ROP requiring laser surgery					X			
Hyperbilirubinemia requiring exchange transfusion					X			
Laboratory Values								
AST		X	X	X	X	X	X	X
ALT		X	X	X	X	X	X	X
GGT		X	X	X	X	X	X	X
Direct bilirubin		X	X	X	X	X	X	X
WBC count		X	X	X	X	X	X	X
Neutrophil count		X	X	X	X	X	X	X
Hematocrit		X	X	X	X	X	X	X
Platelets		X	X	X	X	X	X	X
BUN		X	X	X	X	X	X	X
Creatinine		X	X	X	X	X	X	X
Glucose		X	X	X	X	X	X	X
Sodium		X	X	X	X	X	X	X
Potassium		X	X	X	X	X	X	X
Calcium		X	X	X	X	X	X	X
Magnesium		X	X	X	X	X	X	X
Phosphorus		X	X	X	X	X	X	X
Base excess		X	X	X	X	X	X	X
Positive Blood/Urine/CSF Cultures								
Organism		X	X	X	X	X	X	X
Ampicillin Dosing								
Days of administration					X			
Clinical Variables								
Mechanical ventilation					X			
Fraction of inspired oxygen					X			
Concomitant medications					X			

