10.4.2 Objective #2

Severity of diagnoses and laboratory values will be assigned according to predetermined definitions (see Appendix tables 4 and 5). A diagnosis (Appendix table 4) will be attributed to ampicillin if it was first made on a day that the infant was exposed to ampicillin. A laboratory abnormality (Appendix table 5) will be attributed to ampicillin if it occurred on a day that the infant was exposed to ampicillin or one day after exposure to ampicillin. For the cohort of patients from the PPRU Antimicrobial PK in High Risk Infants study enrolled at Reda, the frequency of diagnoses and laboratory abnormalities attributed to ampicillin will be described using standard summary statistics. For the patients exposed to ampicillin in the Pediatrix database, the frequency of diagnoses and laboratory abnormalities attributed to ampicillin will be compared to those not attributed to ampicillin. Multivariable logistic regression analyses will be performed to evaluate the association between diagnoses and laboratory abnormalities and ampicillin controlling for clinical factors associated with poor outcome in infants such as mechanical ventilation, inotropic support, and demographic features including race, gender, gestational and postnatal age. Outlier diagnostics and evaluation for multicollinearity will be performed using standard techniques. The full model containing all clinically relevant variables listed above will be compared to scaled down models using likelihood ratio tests, and the most parsimonious model that fits the data will be used for analysis. The odds of a diagnosis or laboratory abnormality occurring on a day the infant was exposed to ampicillin will be compared to the odds of occurrence on a day the infant was not exposed to ampicillin. Odds ratios and 95% confidence intervals derived from this model will be reported.

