19 APPENDIX

Table 4. Diagnoses

Body System	Diagnoses	Serious Diagnoses
Gastrointestinal	Medical NEC	Surgical NEC
		Focal intestinal perforation
Neurologic	Grade II IVH	Grade III or IV IVH
	Periventricular leukomalacia	Cystic periventricular leukomalacia
		Seizure
Cardiovascular	PDA requiring medical treatment	PDA requiring surgical treatment
	Hypotension requiring pressors	Cardiorespiratory arrest
	Tachycardia	
Ophthalmology		ROP requiring laser surgery
Hematology		Hyperbilirubinemia requiring exchange transfusion
Dermatology	Rash	
Respiratory	Tachypnea	

IVH=intraventricular hemorrhage
 PDA=patent ductus arteriosus

NEC=necrotizing enterocolitis
 ROP=retinopathy of prematurity

Table 5. Laboratory Values

Laboratory Values	Abnormality	Serious Abnormality
Serum Electrolytes		
Hypoglycemia	< 40 mg/dL	< 20 mg/dL
Hyperglycemia	> 250 mg/dL	> 400 mg/dL
Hyponatremia	< 125 mmol/L	< 115 mmol/L
Hypernatremia	> 150 mmol/L	> 160 mmol/L
Hyperkalemia	> 6 mmol/L	> 7.5 mmol/L
Hypokalemia	< 3 mmol/L	< 2.5 mmol/L
Hypercalcemia (iCa)	> 12.5 mg/dL (>1.5 mmol/L)	> 13.5 mg/dL (>1.6 mmol/L)
Hypocalcemia (iCa)	< 6.0 mg/dL (<0.9 mmol/L)	< 5.0 mg/dL (< 0.8 mmol/L)
Hypermagnesemia	> 3.5 mg/dL	> 4.5 mg/dL
Hypomagnesemia	< 1.5 mg/dL	< 1.2 mg/dL
Hyperphosphatemia	> 9.5 mg/dL	> 10.5 mg/dL
Hypophosphatemia	< 3.5 mg/dL	< 2.5 mg/dL
Base Excess	< -10 mmol/L	< -15 mmol/L
Renal Dysfunction		
Elevated BUN	> 70 mg/dL	> 100 mg/dL
Elevated Creatinine	> 1.7 mg/dL	> 3.0 mg/dL
Liver Dysfunction		
Elevated AST	> 5 x upper limit of normal	> 10 x upper limit of normal
Elevated ALT	> 5 x upper limit of normal	> 10 x upper limit of normal
Elevated GGT	> 5 x upper limit of normal	> 10 x upper limit of normal
Direct bilirubin	> 5 mg/dL	>10 mg/dL
Complete Blood Count		
Leukocytosis	> 25,000/mm ³	> 40,000/mm ³
Leukopenia	< 5000/mm ³	< 2000/mm ³
Neutropenia	< 500/mm ³	< 100/mm ³
Thrombocytopenia	< 100/mm ³	< 30/mm ³
Thrombocytosis	> 600,000/mm ³	> 1,000,000/mm ³

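### Chart review: Table 2 collects the laboratory values for only 8 of the 24 Table 5 abnormalities that section 10.4.2 sets as its outcomes

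*Protocol*

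**What the plan says.** Section 10.4.2 of the protocol starts with rules for Objective #2 as a whole, before it separates the two safety sources: "Severity of diagnoses and laboratory values will be assigned according to predetermined definitions (see Appendix tables 4 and 5". It ties the laboratory outcome to one list: "A laboratory abnormality (Appendix table 5) will be attributed to ampicillin if it occurred on a day that the infant was exposed to ampicillin", or on the following day. Only then does it turn to the PPRU chart-review cohort, for which "the frequency of diagnoses and laboratory abnormalities attributed to ampicillin will be described using standard summary statistics".

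The data for that cohort are fixed in section 6.1.2.1: "Data will be extracted from the medical record of participants enrolled at Redacted in the PPRU Antimicrobial PK in High Risk Infants study". The list follows: "The following clinical and demographic variables will be included in addition to date of birth, gestation age, race, ethnicity, sex, and birth weight (Table 2". Under the title "Table 2: Variables Collected for Redacted Safety Study" the laboratory rows are AST, ALT, WBC count, hematocrit, platelets, BUN and creatinine. Apart from ampicillin dosing there is no medication row.

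The corresponding list in section 6.1.2.2, "Table 3: Variables Collected for Pediatrix Safety Study", has the same seven laboratory rows and ten more: GGT, direct bilirubin, neutrophil count, glucose, sodium, potassium, calcium, magnesium, phosphorus and base excess. It also has a concomitant-medication row.

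Appendix Table 4 gives one cardiovascular diagnosis as "Hypotension requiring pressors". Tables 2 and 3 both list hypotension without that qualifier.

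**The concern.** The outcome list and the collection list for the same cohort are both fixed in this protocol, and they do not match. An analysis plan written later cannot summarise values that were never abstracted. Section 13 says the data collection forms for the chart review are derived from the eCRFs, so an eCRF built to Table 2 would carry the gap straight into the data.

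The chart-review report would then say nothing on neutropenia, direct hyperbilirubinemia, or any glucose, electrolyte or acid-base abnormality. A reader who takes section 10.4.2 at its word, and expects the Table 5 list, could take that silence to mean that no such events were found.

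**Working it through.** The protocol states no figure on this point, so the check is a count. Each Table 5 abnormality was matched to the laboratory variable it needs, and that variable was looked up in Tables 2 and 3.

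| Table 5 block | Rows | Supported by Table 2 | Not supported by Table 2 | Supported by Table 3 |
|---|---|---|---|---|
| Glucose, electrolytes, base excess | 13 | 0 | 13 | 13 |
| Renal | 2 | 2 (BUN, creatinine) | 0 | 2 |
| Liver | 4 | 2 (AST, ALT) | 2 (GGT, direct bilirubin) | 4 |
| Blood count | 5 | 4 (high and low WBC, high and low platelets) | 1 (neutropenia) | 5 |
| Total | 24 | 8 | 16 | 24 |

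- Rows: 13 + 2 + 4 + 5 = 24.
- Supported by Table 2: 0 + 2 + 2 + 4 = 8, and 8/24 = 33%.
- Not supported: 13 + 0 + 2 + 1 = 16, and 16/24 = 67%.

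By analyte, the 24 rows need 7 + 2 + 4 + 3 = 16 distinct variables. Table 2 has 6 of them; its seventh laboratory row, hematocrit, has no Table 5 entry. The shortfall is 16 − 6 = 10, exactly the ten analytes that Table 3 has and Table 2 lacks. Adding them raises coverage from 8/24 to 24/24.

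Diagnoses: Table 4 has 17 entries and Table 2 has 17 adverse-event rows. Sixteen agree. The exception is hypotension, where Table 4 adds the pressor requirement.

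Extra abstraction: Table 2 has seven day columns for laboratory values (−3, −2, −1, on ampicillin, +1, +2, +3).
- Full window: 10 analytes × 7 columns = 70 cells per infant, and 70 × 60 = 4,200 in all.
- Only the two columns the attribution rule uses: 10 × 2 = 20 per infant, and 20 × 60 = 1,200 in all.

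Both totals rise when a course lasts several days, because the on-ampicillin column then stands for more than one day.

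**The case against.** The best defence is that Appendix Tables 4 and 5 are a grading key for whatever each source happens to hold, not a list of required outcomes. Tables 2 and 3 were evidently drawn up source by source: Table 2 has doses in mg, physical examination and antimicrobial sensitivities that Table 3 lacks, and hematocrit is collected in both without any Table 5 row. This reading is possible, but section 10.4.2 does not state it. It defines the reported abnormality by Table 5 and promises its frequency without limit. If a reduced panel was meant, one sentence should say so.

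It is also fair to say that the stakes are modest. The cohort is about 60 infants and is only described. The modelling is done in Pediatrix, with about 400,000 exposed infants and every Table 5 analyte collected. That stands.

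The chart review does record dose in mg and dose time, where Table 3 has only days of administration. This adds little weight here, since the attribution rule works by day.

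On hypotension, a reader might infer that the chart-review rate would rest on a broader definition than the Pediatrix rate, so that the two could not be compared. The documents do not support this. Tables 2 and 3 use the same unqualified word, Table 4 governs both cohorts, and an abstractor with the full medical record could apply the Table 4 definition. Table 3 does have a concomitant-medication row, but nothing says it will be used to derive hypotension. Nor does the protocol plan any comparison of the chart review with Pediatrix.

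**Conclusion.** The mismatch is real. Followed as written, the chart review can produce 8 of its 24 predefined laboratory abnormalities and cannot produce the other 16 (67%).

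It would go too far to conclude that the chart review cannot report its outcomes at all: the 8 laboratory abnormalities and at least 16 of the 17 diagnoses remain reportable. It would also be wrong to infer damage to the Pediatrix odds ratios, which do not use Table 2.

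The hypotension wording is a secondary inconsistency that touches Tables 2 and 3 alike.

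The conclusion assumes that the eCRF follows Table 2. The count of 8 assumes that upper limits of normal are available to grade AST and ALT. The 24 of 24 for Table 3 assumes that its calcium row includes the ionized values that Table 5 refers to. The count of 16 for Table 2 does not depend on the last two assumptions. The point should be settled before abstraction starts, but it does not threaten the main comparative safety analysis.

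**What to change.** Choose one of two routes before charts are abstracted.

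1. Add to Table 2 and its eCRF the ten analytes already in Table 3: GGT, direct bilirubin, neutrophil count, glucose, sodium, potassium, calcium, magnesium, phosphorus and base excess. On-ampicillin days and day +1 are the minimum, since the attribution rule uses those days. Days −3 to +3 are preferable, to match the other Table 2 laboratory values. The cost is moderate extra abstraction from charts already being opened, about 70 day-cells per infant for the full window and more for longer courses. It needs no patient contact and no new test.

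2. If that is declined, state in section 10.4.2 that for the chart-review cohort only the 8 derivable abnormalities are reported, list them, and say that the other 16 were not collected. This costs a sentence or two, but leaves this cohort uninformative on two-thirds of the predefined laboratory list.

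Under either route, reconcile the hypotension row in Tables 2 and 3 with Table 4, so that the form, the extraction and the appendix use one definition. If the Table 4 wording is kept, a yes/no field for pressor use in Table 2 would make it verifiable.

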3 OBJECTIVES

3.1 Study Outcome Measures

The purpose of this study is to evaluate the PK and safety profile of ampicillin administered to infants per standard of care by their treating caregiver. The PK of ampicillin will be evaluated through the analysis and evaluation of PK data obtained from 3 PK studies of ampicillin in infants (PPRU, POPS, Redac ampicillin study). The safety profile of ampicillin will be evaluated through analysis and interpretation of safety data available from a subset of infants enrolled in one of the PK studies (PPRU Antimicrobial Pharmacokinetics (PK) in Premature Infants Trial at Reda) and from data collected on all infants administered ampicillin per standard of care by their caregiver while admitted in one of the 323 NICUs managed by the Pediatrix Medical Group.

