5.1.2 Objective #2

All infants who received ampicillin while enrolled in the PPRU Antimicrobial Pharmacokinetics (PK) in Premature Infants Trial at Redacted and infants treated in a NICU managed by the Pediatrix Medical Group between 1997 and 2010 who did or did not receive ampicillin per standard of care. This will include approximately 60 infants from the PPRU study and approximately 400,000 infants from the Pediatrix database.

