10.1.2 Objective #2

We anticipate data from approximately 400,000 infants who received ampicillin and 300,000 infants who did not receive ampicillin in the Pediatrix Medical Group Database. In addition, retrospective chart review will be performed on an additional 60 infants who received ampicillin while enrolled in the PPRU study at Redacted.

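### The protocol gives conflicting populations for the Pediatrix odds ratio and, read as written, pools off-drug days of treated infants with days of never-treated infants

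*Protocol*

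**What the plan says.** Section 10.4.2 of the protocol describes two Pediatrix analyses of the same diagnoses and laboratory abnormalities.

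- **Frequency comparison.** It is limited to treated infants: "For the patients exposed to ampicillin in the Pediatrix database, the frequency of diagnoses and laboratory abnormalities attributed to ampicillin will be compared" with those not attributed to the drug.
- **Multivariable logistic regression.** The odds of an event on an exposed day "will be compared to the odds of occurrence on a day the infant was not exposed to ampicillin". The odds ratio and its 95% confidence interval come from this model. The sentence does not say whether the unexposed days belong to treated infants only or to every infant in the database.

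The other sections do not agree on the population:

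- The synopsis describes infants who received ampicillin and gives about 400,000 for the safety analysis.
- Section 3.1 refers to "data collected on all infants administered ampicillin per standard of care by their caregiver while admitted in one of the 323 NICUs" managed by the group.
- Section 4 reviews every infant in the database, on drug versus not on drug.
- Section 5.1.2 takes infants "who did or did not receive ampicillin per standard of care", yet counts "approximately 400,000 infants from the Pediatrix database".
- Section 5.2 admits all infants discharged from 1997 to 2010, with no exposure condition and no exclusions.
- Section 10.1.2 expects "approximately 400,000 infants who received ampicillin and 300,000 infants who did not receive ampicillin in the Pediatrix Medical Group Database", and no section names an analysis for the second group.

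**The concern.** An analyst who follows the synopsis and section 3.1 would build a dataset of treated infants. One who follows 5.2 and 10.1.2 would add some 300,000 infants who never received the drug. Each dataset agrees with part of the protocol, and each gives a different reference for the only effect estimate that the safety objective promises.

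Under the second reading, one odds ratio carries two contrasts. The first compares days on and off drug among infants who were treated at some point. The second compares infants whom clinicians chose to treat with infants whom they did not, which is confounding by indication. Ever-treated status is not among the named adjustment variables, and the model-reduction step may drop some of those that are named. A raised odds ratio could then reflect who was treated rather than the drug. The data already exist and nothing is masked, so fixing the contrast in advance is the main safeguard.

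**Working it through.** **1. Counts.** Section 10.1.2 gives 400,000 + 300,000 = 700,000 Pediatrix infants. The synopsis and section 5.1.2 give about 400,000. In 5.1.2 that figure covers treated and untreated infants together; in 10.1.2 it is the treated group alone. Both cannot hold.

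**2. Can never-treated infants enter the regression?** Under 5.2 they are included, and every one of their days meets the reference definition in 10.4.2. Logistic regression as described does not condition on the infant, so nothing in the stated method removes them. Table 3 points the other way: its windows are set around an ampicillin course, which a never-treated infant lacks. The text does not settle the question.

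**3. What pooling does to the odds ratio.** The protocol gives no event rates or day counts, so there is no stated figure to reproduce. All inputs below except the infant counts are assumptions.

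- *p* = 0.01: daily risk in treated infants, the same on and off drug (no drug effect).
- *f*: daily risk in never-treated infants relative to *p*.
- *a*: off-drug days per treated infant; *b*: days per never-treated infant.

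Reference risk: q = (400,000·a·p + 300,000·b·f·p) / (400,000·a + 300,000·b)

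Odds ratio: OR = [p/(1−p)] / [q/(1−q)]

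Worked case, a = 5, b = 10, f = 0.5: the reference has 2,000,000 + 3,000,000 days, and q = (20,000 + 15,000)/5,000,000 = 0.0070. So OR = 0.010101/0.007049 = 1.43.

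| a, b | never-treated share of reference days | f = 1 | f = 0.5 | f = 0.25 |
|---|---|---|---|---|
| 5, 10 | 3.0/5.0 million = 60% | 1.00 | 1.43 | 1.83 |
| 15, 10 | 3.0/9.0 million = 33% | 1.00 | 1.20 | 1.34 |
| 30, 5 | 1.5/13.5 million = 11% | 1.00 | 1.06 | 1.09 |

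With treated infants only, q = p and the OR is 1.00 in every row.

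**4. Does adjustment remove it?** Within any stratum of the covariates the same formula applies, with that stratum's own mix of days and its own *f*. Adjustment therefore helps only as far as it brings *f* within strata towards 1. An expected-count logistic regression with one indicator per postnatal day illustrates this. It assumed stays of 15 days (treated) and 5 days (never treated), twice the baseline risk in treated infants, and equal on- and off-drug risk. The null odds ratio was 1.00 in treated infants and 1.39 with pooled reference days. Over baseline risks 1.5 to 3 times higher in treated infants, the pooled value ran from 1.21 to 1.60. With equal baseline risk both were 1.00. Ventilation and inotropic support were not modelled and could narrow the gap.

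**5. Would sampling error hide it?** Take 3 on-drug days per treated infant (1.2 million days) and independent days. At *p* = 0.01 there are 12,000 on-drug events. In the smallest artefact above (30, 5; f = 0.5) there are 127,500 reference events. An odds ratio beyond exp(1.96·√(1/12,000 + 1/127,500)) = 1.02 excludes 1, so 1.06 would too. At *p* = 0.001 the limit is exp(1.96·√(1/1,200 + 1/12,750)) = 1.06, about equal to that artefact, while the artefacts of 1.20 and above clear their limits (at most 1.07).

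**The case against.** There is a fair case for reading the regression as confined to treated infants. It follows directly on the sentence about exposed patients, and its closing comparison speaks of the same infant exposed and not exposed. Section 3.1 and Table 3 fit that reading, and the synopsis total equals the treated count in 10.1.2. A frequency table followed by an adjusted model is also an ordinary sequence, and details may sit in an analysis plan that is not shown. This makes the treated-only reading tenable, but it leaves the 300,000 infants in 10.1.2 without a role and sections 4, 5.1.2 and 5.2 in need of correction. An analysis plan cannot follow both sets of sections.

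Several stronger readings might be inferred and are not supported.

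- **That the two populations give opposite answers.** The table in the working shows null against apparent harm, not reversal. A change of direction also needs off-drug days to be riskier than on-drug days. With daily risks of 1.0% on drug, 1.2% off drug and 0.2% never treated, and 5 days each for *a* and *b*, the crude values are 0.83 and 1.30. With 0.9% in never-treated infants there is no reversal. Opposite directions appeared in 10 of 24 scenarios adjusted for postnatal day, one only marginally. The protocol has no figures to say which scenario applies.
- **That every odds ratio would be inflated.** This holds only if never-treated infants are at lower risk after adjustment.
- **That one comparison is decisive.** The protocol names no primary contrast and no decision rule for this objective.
- **That restriction to treated infants gives a clean within-infant estimate.** Without conditioning on the infant it still pools across infants. If off-drug days carry 1.2 or 1.5 times the on-drug risk, it gives 0.83 or about 0.66 with no drug effect.

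**Conclusion.** The point holds as a conflict within the protocol. Its sections name different populations and different totals for one odds ratio, and the reference in 10.4.2, taken with 5.2 and 10.1.2, pools two kinds of unexposed day. The direction of the resulting bias is conditional: relative to treated infants alone, pooling raises the odds ratio if never-treated infants have a lower daily risk that the covariates miss.

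The sizes, 1.06 to 1.43 at half the risk and 1.09 to 1.83 at a quarter, are unadjusted illustrations. They rest on assumed day counts, constant daily risk and equal on- and off-drug risk in treated infants. They show that the choice can matter, not what the Pediatrix data would show. The change should be made before the analysis, since it is cheap and the contrast is otherwise left open with the data in hand.

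**What to change.** - In 10.4.2, state one reference set for the reported odds ratio, and do not pool the two kinds of unexposed day.
- Fit a three-level exposure variable: exposed day; unexposed day in an ever-treated infant; day in a never-treated infant. Report exposed days against each of the other two levels separately, each labelled for what it compares.
- Label the frequency comparison descriptive.
- Reconcile the populations and counts in the synopsis and sections 3.1, 4, 5.1.2, 5.2 and 10.1.2, and say what the 300,000 untreated infants are for.

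The cost is wording, one extra contrast and fewer reference days per odds ratio, which matters little with about 400,000 treated infants. No new data are needed. The change separates the between-infant component from the on/off comparison. It does not remove confounding by when in the stay the drug was given, and the report should say so.

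### Section 10.4.2 takes confidence intervals from a day-level logistic model with no allowance for repeated days per infant, so those for the 24 laboratory abnormalities are invalid, usually too narrow

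*Protocol*

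**What the plan says.** Everything that matters here is in Protocol section 10.4.2, supported by Tables 3 to 5.

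- Unit of comparison: the day. "The odds of a diagnosis or laboratory abnormality occurring on a day the infant was exposed to ampicillin will be compared" with the odds on a day without exposure.
- Model: "Multivariable logistic regression analyses will be performed to evaluate the association between diagnoses and laboratory abnormalities and ampicillin", adjusting for mechanical ventilation, inotropic support, race, gender, gestational age and postnatal age.
- Model selection: the full model is "compared to scaled down models using likelihood ratio tests, and the most parsimonious model that fits the data will be used for analysis".
- Inference: "Odds ratios and 95% confidence intervals derived from this model will be reported".
- Diagnoses (17 in Appendix Table 4): attributed to ampicillin "if it was first made on a day that the infant was exposed to ampicillin". Table 3 also labels them as new onset. Each infant can therefore supply at most one event per diagnosis.
- Laboratory abnormalities (24 in Appendix Table 5, each at two grades): attributed "if it occurred on a day that the infant was exposed to ampicillin or one day after exposure to ampicillin". No first-occurrence rule applies.

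Table 3 collects laboratory values on three days before the course, during it and on three days after it, so one infant supplies many rows. The section names no GEE, random effect, conditional likelihood or cluster-robust variance. It does not say whether an infant's days after a first diagnosis stay in the comparison.

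**The concern.** An ordinary logistic model treats every row as independent. Here the rows are days nested in infants. A raised creatinine or low platelet count usually lasts several days, so one episode can be entered as several events. Ampicillin is also given in runs of consecutive days. When outcome and exposure are both correlated within an infant, the data hold less information about the exposure effect than the row count suggests, and the model's standard errors are usually too small.

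These odds ratios and intervals are the main comparative safety output of Objective #2. With 24 laboratory abnormalities at two grades each, intervals that exclude 1 too often would produce apparent laboratory signals for a drug that section 2.1.1 calls the most commonly administered in the NICU. The parsimony step is affected too, because a likelihood ratio test on an independent-rows likelihood has the wrong reference distribution for clustered rows.

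**Working it through.** The protocol gives no intraclass correlation (ICC), event rate, days per infant or precision target for Objective #2, so there is no figure of its own to reproduce. All correlations, stays and hazards below are assumptions. The exposed share follows from section 10.1.2: 400,000 / (400,000 + 300,000) = 57%.

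**1. Approximate size.** With m days per infant, outcome ICC ρy and exposure ICC ρx, the variance inflation is D = 1 + (m − 1)·ρx·ρy. A nominal 95% interval then covers 2Φ(1.96/√D) − 1.

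- m = 10, ρy = 0.2, ρx = 0.5: D = 1 + 9 × 0.1 = 1.90, coverage 85%.
- Same m and ρy, with ρx = 0.2 or 1.0: D = 1.36 or 2.80, coverage 91% or 76%.
- Over m = 5 to 40, ρy = 0.05 to 0.4 and ρx = 0.2 to 1: D runs from 1.04 to 16.6, coverage from 94.5% to 37%.

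The formula gives inflation only when ρx is positive. If exposure varies mainly within infants, the error can reverse.

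**2. Laboratory outcome, simulated with no drug effect.** The ratio is true variance over model variance.

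| Cohort and window | Within-infant pattern | Ratio | Rejection at 5% |
|---|---|---|---|
| 14 days, 57% exposed | carry-over 0.7 | 2.8 | 25% |
| 14 days, 57% exposed | carry-over 0.4 | 1.9 | 13.5% |
| 14 days, all exposed | carry-over 0.7 | 2.1 | 17% |
| 14 days, all exposed | carry-over 0.4 | 1.8 | 13% |
| Course ± 3 days, all exposed | carry-over 0.4 to 0.7 | 1.26 to 1.29 | not recorded |
| Course ± 3 days, all exposed | infant effect only | 0.87 to 0.93 | not recorded |

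The 14-day rows use 3,000 infants, courses of 2, 3 or 7 days, 5% daily prevalence and 400 runs. Infant-clustered variance gave about 3% to 7% rejection in those settings. A further set of runs with persistence 0.4 to 0.7 gave ratios of 1.4 to 2.7 and rejection of 10% to 24%, returning to about 5% with clustering. The normal approximation 2[1 − Φ(1.96/√ratio)] agrees: 9.8% at 1.4 and 23% at 2.7.

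A separate run used a random infant intercept, 1,500 infants, 15 days and 3/7 never exposed. With intercept SD 1, the model standard error was 0.072 against an empirical 0.082 (ratio (0.082/0.072)² ≈ 1.3), with 91% coverage. With SD 2 it was 0.054 against 0.085 (ratio ≈ 2.5), with 81% coverage. Clustering restored 94% to 96%. The mean odds ratio stayed at 0.99 to 1.00, so the interval is at fault and not the estimate. A between-infant effect alone can therefore still narrow intervals when never-exposed infants are in the comparison, because exposure is then partly a between-infant contrast.

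**3. First diagnoses.** If each infant contributes days up to and including the first diagnosis, the day-level model is a discrete-time hazard model. In 200 runs without postnatal age (2,000 infants, 20 days), it gave odds ratios of 1.00 to 1.01 (true value 1) and 95% to 97% coverage with ordinary standard errors.

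If later days stayed in as non-events, then with constant daily hazard h, exposure on the first k of L days and no true effect, the mean daily probabilities are pE = [1 − (1 − h)^k]/k and pU = [(1 − h)^k − (1 − h)^L]/(L − k). For h = 0.02, k = 3, L = 20: pE = 0.0588/3 = 0.01960, pU = 0.2736/17 = 0.01609, and the odds ratio is 1.22. For h = 0.0005, 0.005 and 0.05 it is 1.005, 1.05 and 1.65. These figures are unadjusted. In simulation at h = 0.05, keeping all days gave 1.41 without postnatal age and 1.01 with it.

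**The case against.** Several objections have force.

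- *The SAP may deal with this.* It may, and it is not shown. But the protocol itself fixes the day as the unit, the model, the selection test and the source of the intervals, and nothing in it points to clustered inference.
- *Likelihood ratio tests do not imply independent rows.* Correct. Mixed and conditional logistic models have valid likelihood ratio tests. The problem arises only if the named model is fitted in its ordinary form, which is the natural reading of the text.
- *Size and direction are not known.* This stands. Persistence and stay are assumed. A window of three days either side of the course, in exposed infants only, gives much less inflation, and with an infant effect alone the intervals are slightly too wide. Section 10.1.2 counts never-exposed infants, while part of section 10.4.2 speaks of exposed infants, so the cohort structure that drives the size is itself unclear.
- *This is a descriptive safety review with no decision rule.* True, but it reports odds ratios with intervals, and readers will take an interval that excludes 1 as a signal.

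A reader might also infer that the plan keeps days after a first diagnosis and so biases those odds ratios upward. The text does not say this; it is silent. The bias would be negligible for rare diagnoses and is largely removed by the planned postnatal-age term. Its upward direction also needs treatment to start when observation starts: with three pre-course days at risk, the odds ratio is 0.999 at 10% cumulative incidence and 0.992 to 0.993 at 30%.

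**Conclusion.** The point holds for the 24 laboratory abnormalities. As written, their intervals and the likelihood-ratio model selection make no allowance for repeated days and are invalid. They are usually too narrow: about 1.4- to 2.7-fold variance understatement and 10% to 24% rejection at nominal 5%, given assumed persistence of 0.4 to 0.7. Individual settings in that persistence range gave ratios from 1.26 to 2.8. With only a between-infant effect and exposure varying within infants, the intervals are near nominal or slightly too wide. The laboratory odds ratios themselves were not biased in these checks.

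It does not extend to all 41 outcomes. The 17 first-only diagnoses need no clustering correction for repeated days if infants leave the risk set at diagnosis. What is needed there is a stated rule, plus protection of the postnatal-age term, which the parsimony step could drop. Section 3.1 describes infants "while admitted in one of the 323 NICUs managed by the Pediatrix Medical Group", and a reader might infer a demonstrated centre-clustering error. Its effect was not quantified, so no claim is made about it.

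**What to change.** In section 10.4.2:

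1. For laboratory abnormalities, specify logistic GEE or infant-clustered robust variance, with Wald or score tests in place of likelihood ratio tests. Alternatively, specify a conditional or mixed logistic model with its own likelihood-based tests.
2. For diagnoses, state that each infant contributes days only up to and including the first occurrence of that diagnosis. Ordinary logistic regression may then stand as regards repeated days.
3. Keep postnatal age in the diagnosis models whatever the parsimony step finds. If later days were retained and that term dropped, odds ratios for common early diagnoses would be biased.

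The cost is wording and analysis code; no new data are needed. The downside is that laboratory intervals will generally be wider.
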